3.1 Study Population

The SCP Observational Cohort study will enroll either patients undergoing SCP or patients who have already had the SCP procedure for the treatment of BMLs where bone void filler is placed at the site of the BML (defect).

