4.1 Subject Eligibility

Enrollment will be based on the treating physician's standard of care and the following criteria:

1. Surgeon considers patient appropriate for SCP procedure.
2. Patient has agreed to undergo the SCP procedure or has already undergone the procedure.
3. Subject is willing and able to sign a written consent form.
4. The subject has the mental capacity and the willingness to contribute follow-up outcome data.
5. Patient is willing and able to complete outcome forms in person or by phone, email or regular mail.

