4.2 Subject Enrollment

All patients considered for the SCP procedure by the investigator or who have had the SCP procedure will be invited to participate in the study. Patients expressing an interest in participation will proceed with the informed consent process. No study activities will be performed prior to patient signature of the informed consent form. If the patient does not sign the informed consent, the patient will still undergo the SCP procedure, but they will not be included in the observational cohort study. Should a patient not undergo SCP, the patient will not be enrolled in the observational cohort study and will be reported as a screen fail. The enrollment status for each patient considered in the study will be appropriately documented on a screening log.

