4.4.2 Operative Procedures

The surgical process is to follow site standard of care.

Data collected during the operative procedure of the Subject is listed in Table 2.

Table 2: Operative Data Collection

| Form 3—Surgical Evaluation & Details | |
|---|--|
| Evaluation | Details of Evaluation |
| Imaging Evaluation | Baseline MRI and Standing Alignment X-Ray dates. |
| Standing Alignment | Patient's standing alignment. |
| Bone Marrow Edema Location | Surgeon must indicate locations of bone marrow edema on MRI. |
| Surgical Procedure Details | Description of Subject's operative procedure including such items as findings and treatments, operative times and diagnoses. |
| Adverse Event (if applicable) | Description of adverse events occurring during the operative procedure, if applicable . |

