5.1 Adverse Events

An adverse event (AE) is defined as an untoward medical occurrence, unintended disease or injury, or untoward clinical signs (or change or worsening of a pre-existing medical condition) in a patient, which may or may not have an association with the

device. In addition an adverse device effect is defined as ‘any untoward and unintended response to a medical device’.

For this study, **only AEs which are possibly or definitely related to the device or procedure will be reported to the sponsor.** The determination whether the AE is related to the device or procedure will be based upon whether a causal relationship between the device or procedure and the AE is at least a reasonable possibility, i.e. the relationship cannot be ruled out. A causal relationship cannot be ruled out if, in the medical judgment of the investigator, the effect follows a reasonable temporal association with the use of the device and/or is confirmed by the improvement of the effect upon discontinuation of the clinical use of the device, and/or the effect is not reasonably explained by the Subject’s clinical state.

Relationship to study device or procedure should be rated as follows:

1. **None** (definitely not related): there is no relationship between study device or procedure and the event.
2. **Possible** (remote possibility, possibly, or probably related): the relationship between study device or procedure could exist if there is no contradicting evidence that can reasonably explain the Subject’s condition.
3. **Definite** (definitely related): the relationship between study device or procedure and event does exist and is confirmed upon further investigation by the investigator.

Pre-existing medical conditions or symptoms reported prior to device implantation are not to be recorded as AEs. In the event there is an exacerbation of the pre-existing medical condition or symptoms (due to the device or study related procedure), then an AE must be reported.

AEs are reported beginning from time of surgery until Subject participation has ended (study completed or Subject withdrawn). AEs must be followed to resolution or until the study completion or Subject withdrawal.

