Subjects should be encouraged to report AEs spontaneously and may volunteer AE information at any time. At each evaluation, the investigator will determine whether an AE has occurred. If it is determined that an AE has occurred, the investigator should obtain all the information required to complete the appropriate AE form(s). If an event occurs at an outside institution, the investigator should attempt to obtain, if possible, required AE information to report to the Sponsor.

The investigator will record the nature, severity, treatment and outcome of the AE, and will determine their association to the device or the study procedure.

The following categories of AE severity are to be used:

1. **Mild:** awareness of a sign, symptom or event that is easily tolerated and transient in nature with minimal or no impairment to normal activity.
2. **Moderate:** moderate symptoms that are poorly tolerated, sustained, interfere with normal activity and require medical attention.
3. **Severe:** symptom(s) require intervention, and the activities of daily living are significantly altered.

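### AE reporting starts at surgery for every subject, but the plan has no dedicated step to find related AEs between the operation and consent in subjects who enrol afterwards, so short-term AE frequency may be understated by an unknown amount.

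*Combined protocol and SAP*

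**What the plan says.** All references are to the Combined protocol and SAP.

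- **Who enters.** Section 3.1 states that the study "will enroll either patients undergoing SCP or patients who have already had the SCP procedure", and the second criterion in Section 4.1 reads "Patient has agreed to undergo the SCP procedure or has already undergone the procedure". Neither sets a maximum time from surgery to consent.
- **When study work may begin.** Section 4.2: "No study activities will be performed prior to patient signature of the informed consent form".
- **Reporting window.** Section 5.1: "AEs are reported beginning from time of surgery until Subject participation has ended". It gives no separate start for subjects enrolled after surgery. Only events judged possibly or definitely related are sent to the sponsor.
- **How events are found.** Section 5.1 gives two routes: "At each evaluation, the investigator will determine whether an AE has occurred", and "Subjects should be encouraged to report AEs spontaneously and may volunteer AE information at any time". Form 3 (Section 4.4.2) adds a "Description of adverse events occurring during the operative procedure".
- **When evaluations fall.** Section 4.4.3 schedules Form 4 at eight fixed times from 6 weeks to 5 years after surgery. Section 4.4 allows it to be completed remotely, with no office visit required. Its AE entry is completed only if applicable, and it also has an item on surgical and non-surgical procedures.
- **Purpose.** Section 3 names short-term as well as long-term safety. Neither Section 3 nor Section 4.5 defines an AE rate or a denominator.

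**The concern.** The window in Section 5.1 is the same for everyone, but the means of filling it are not. A subject who consents before surgery can be evaluated at 6 weeks, 3 months and 6 months, close to any early event. A subject who consents 2.5 years after surgery has a first scheduled evaluation at 3 years. The plan does not say who should then establish what happened in the first 2.5 years, from what source, or how the answer is recorded.

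Other parts of the plan suggest that the collection steps were written for subjects consented before surgery. Section 4.4.1 asks for the Table 1 data from each enrolled subject ahead of the operation, which a patient enrolled afterwards cannot supply in that order. The documents do not say whether Form 3 is completed retrospectively for such a patient.

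At stake is the short-term safety result. If the two kinds of subject are pooled, early events in one group are sought close to when they happen, while those in the other rest on recall, an unprompted report, or a chart check that nobody is assigned. As the plan describes the AE entry, a blank for the earlier interval may mean that no event occurred or that nobody asked. Missed events can only lower the observed frequency.

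**Working it through.** The plan states no AE frequency, so there is no figure to reproduce. The check has two parts.

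**1. Which step reaches the interval from the end of the operation to consent, for a subject enrolled afterwards?**

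| Step | Reaches the interval? |
|---|---|
| Form 3 AE entry | No; it covers the operation itself |
| Form 4 visits due before consent | No; Section 4.2 bars them |
| First Form 4 after consent, AE entry | Possibly; no recall period is stated |
| Form 4 procedures item | Possibly, for events that led to a procedure |
| Spontaneous report | Possibly |
| AE review or chart check at enrolment | Not in the plan |

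Three routes could reach the interval, and none is specified to do so.

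**2. How large could the effect be?** Let

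- s = share of the cohort already operated at consent,
- f = share of those subjects' related AEs that fall between surgery and consent,
- m = share of those AEs that are missed.

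Assume the same true risk in both groups and every subject in the denominator. Then

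observed / true = 1 − s × f × m.

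None of s, f, m or the true risk is in the documents, so all values below are assumptions.

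*Milder inputs* (s = 10% to 50%, f = 30% to 60%):

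- All missed (m = 1): from 1 − 0.1 × 0.3 = 0.97 to 1 − 0.5 × 0.6 = 0.70.
- Half missed (m = 0.5): from 1 − 0.1 × 0.3 × 0.5 = 0.985 to 1 − 0.5 × 0.6 × 0.5 = 0.85.
- None missed (m = 0): 1.0.

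With 1000 subjects and an assumed true risk of 10%, the m = 1 range is 1000 × 0.10 × 0.03 = 3 to 1000 × 0.10 × 0.30 = 30 subjects whose event is missed.

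*Harsher inputs.* Suppose consent is uniform over 0 to 5 years after surgery and event times are exponential with mean 0.5 or 1 year, truncated at 5 years. Then f = 1 − E[T]/5. E[T] is 0.50 or 0.966 year, so f = 0.90 or 0.81. With an assumed true risk of 5%:

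| s | f | m | Ratio | 5% reads as |
|---|---|---|---|---|
| 10% | 0.81 | 0.5 | 0.96 | 4.80% |
| 10% | 0.90 | 1 | 0.91 | 4.55% |
| 50% | 0.81 | 0.5 | 0.80 | 3.99% |
| 50% | 0.90 | 1 | 0.55 | 2.75% |
| any | any | 0 | 1.00 | 5.00% |

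The 0.55 row is a worst-case corner. Shorter delays to consent make f smaller and move the ratio towards 1.

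**The case against.** A reader might infer that the interval before consent is excluded or goes unexamined, and that the AE rate therefore reads low. The documents do not support that, for four reasons.

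- The time at which an evaluation takes place is not the period that it covers. Section 5.1 opens the window at surgery and sets no recall limit, so the first evaluation after consent may properly look back to the operation. Section 4.2 bars study work before consent, not questions afterwards about earlier events.
- Other routes exist. The Form 4 procedures item can reveal a re-intervention, and Section 5.2 treats any surgical intervention as a serious event. Section 5.1 also asks the investigator to try to obtain information on events at outside institutions.
- Only form headings are shown. An AE item worded to cover all time since surgery would close much of the gap.
- No AE rate or denominator is defined, so pooling is an assumption. No figure in the documents shows that related events cluster soon after surgery.

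All of this stands. It rules out any claim of exclusion or of a known bias. It does not supply a method. A window that includes the interval assigns nobody to examine it, and a remote form with an if-applicable AE entry does not prompt a chart review. The gap is an unspecified ascertainment step for one identifiable group of subjects.

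**Conclusion.** The point holds as a gap in ascertainment. For subjects who consent after surgery, the plan schedules no dedicated step to find related AEs between the end of the operation and consent. Short-term AE frequency may be understated if these subjects are pooled with those followed from surgery.

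Any bias from missed events is downward. Its size cannot be derived from the documents: on assumed inputs the observed-to-true ratio runs from 1.0 with full look-back to about 0.55 in the worst corner tried. That range rests on equal true risk in both groups, a per-subject proportion with everyone in the denominator, and assumed values for the share already operated, the share of events before consent and the completeness of capture. It shows what is possible and is not an estimate. The plan does not say how an analyst would narrow it afterwards, because no entry is specified to separate an absent event from an unasked question. A change is worthwhile because short-term safety is a stated purpose and the remedy is cheap.

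**What to change.** In Sections 4.4.2 and 5.1, require one AE review at enrolment, after consent, for each subject enrolled after surgery:

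- It covers the time from surgery to the consent date.
- It uses the investigator's own clinic and operative records plus one direct question to the subject.
- The form carries an explicit entry for none and for not done, and events found this way are flagged as retrospective.

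Record the surgery and consent dates for every subject. In Section 4.5, tabulate AEs separately for subjects consented before and after surgery. Base short-term AE frequency on subjects followed from surgery or with a completed look-back.

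The cost is one extra form page, a short chart check per already-operated subject and one table split. The reported AE frequency may come out somewhat higher. Treatment, eligibility and the enrolment goal are unaffected.

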5.2 Serious Adverse Events

A Serious Adverse Event (SAE) is defined as any untoward medical occurrence that:

1. Results in death
2. Is a life-threatening illness or injury
3. Requires inpatient hospitalization or prolongation of existing hospitalization
4. Results in persistent or significant disability/incapacity, or
5. Is a congenital anomaly/birth defect
6. Medical or surgical intervention to prevent life-threatening illness or injury or permanent impairment to a body structure or function.
7. Other serious (Important Medical Events). Report when the event does not fit the other outcomes, but the event may jeopardize the patient and may require medical or surgical intervention (treatment) to prevent one of the other outcomes.

For the purpose of this protocol, **any surgical intervention** is considered a serious adverse event. In case of death, all possible information available, such as autopsy or other post-mortem findings should be provided.

SAEs must be reported to the Sponsor as soon as possible and within 24 hours after the investigator first learns of the event. SAEs are reported to the respective Institutional Review Board (IRB) or Ethics Committee (EC), as per their respective requirements by the site.

6. Missed Follow-up Completion of Questionnaires

If a subject fails to complete the post-operative questionnaires at a follow-up time point, the site should continue to attempt follow-up of the subject through the five year study end point. The subject should only be considered Lost to Follow-Up and exited from the study under the conditions described in section 7.2. There should be at least three documented attempts to contact the subject to obtain follow-up data with any combination of an email reminder via OBERD, a phone call or an IRB approved subject follow-up letter.

7. Discontinuation of Subject Participation

7.1 End of Study/Withdrawal

Study participation may be discontinued through surgical revision (Partial, Total Knee Arthroplasty or total removal of AccuFill), withdrawal of consent, investigator decision or death. All consented Subjects who are withdrawn/discontinued from the study should have an end of study form completed to explain why they are no longer participating in the study. This form should be sent to the Sponsor upon completion and placed in the subject's binder.

7.2 Lost to Follow-Up

If the subject does not complete the required questionnaires through the five year time point and the Investigator or Study Coordinator has attempted to contact that subject at least three times via email reminder through OBERD, a phone call or an IRB approved subject follow-up letter and receives no response, the subject may be deemed to be lost to follow-up. The research staff should have documentation of the attempts to contact the subject. The final attempt to contact the subject will be performed by certified mail and the receipt will be placed in the subject's file. An end of study form must be completed, sent to the Sponsor and also placed in the subject's file.

Should a subject who previously chose to withdraw their consent wish to re-enter the study, a new signed Informed Consent Document will be required. The site may resume follow-up visits as long as they are within the designated visit window.

8. Protocol Adherence

The Investigator(s) agrees to conduct the study in accordance with this protocol. For the purpose of this study, **only** violations that affect the subject's rights, safety, or welfare, or the integrity of the data will be recorded. A log of the violations will be kept within the site's regulatory binder and sent to the Sponsor when any violations have occurred.

A protocol violation can be described as accidental or unintentional change to, or non-compliance with the IRB approved protocol without prior Sponsor and IRB approval. Violations generally increase risk and/or decrease benefit, affects the subject's rights, safety, or welfare, or the integrity of the data. Examples include failure to obtain valid informed consent (e.g., obtained informed consent on an unapproved consent form), loss of laptop/computer that contained identifiable and private information about subjects or not following inclusion/exclusion criteria.

Protocol deviations will **not** be collected for this study nor added to the protocol violation log. A protocol deviation is an accidental or unintentional change to or non-compliance with the

research protocol that does not increase risk or decrease benefit or does not have a significant effect on the subject's rights, safety or welfare, and/or on the integrity of the data. A deviation may be due to the research subject's non-adherence or an unintentional change to or non-compliance with the research protocol on the part of a researcher.

9. Ethical Considerations

9.1 IRB Approval

IRB approval will be obtained prior to patient enrollment at each site. The revocable informed consent form will conform to 21 CFR Part 56, Institutional Review Boards.

9.2 Protection of Patient Confidentiality

All HIPAA requirements for subject confidentiality will be maintained.

Only approved study personnel shall have access to the patient records. None of the specific patient data will be disclosed to persons or organizations not involved in the research. Reports generated will not identify individual patients in any way.

In addition to protection of patient privacy rights, Zimmer Knee Creations will use due diligence to restrict access to this study platform and patient outcomes. Zimmer Knee Creations will maintain exclusive responsibility for study administration and oversight.

Zimmer Knee Creations will complete the development of this observational cohort program; provide training and continuing education on proper methods for data collection, entry and reporting; and oversee compliance with patient privacy rights including HIPAA.

10. Subject Stipends or Payments

Subjects will receive stipends based on each site's respective budget and informed consent form.
